9.7.1.8.3 LABORATORY VALUES

Laboratory results will be summarized using Système International units, as appropriate. For all quantitative parameters listed in Section 9.5.1.5.3, the actual value and the change from baseline to each postbaseline visit and to the end of treatment (defined as the last on-treatment value) will be summarized by visit and treatment group using descriptive statistics. Percentages will be based on the number of subjects with both nonmissing baseline and relevant postbaseline results.

Laboratory test results will be assigned a low/normal/high (LNH) classification according to whether the value was below (L), within (N), or above (H) the laboratory parameter's reference range. Within-treatment comparisons for each laboratory parameter will be based on 3-by-3 tables (shift tables) that compare the baseline LNH classification to the LNH classification at the End of Treatment and the Follow-Up visits. Similar shift tables will also compare the baseline LNH classification to the LNH classification for the highest and lowest value during the treatment period.

Appendix 1 presents the criteria that will be used to identify subjects with treatment-emergent markedly abnormal laboratory values (TEMAV). Except for phosphate, a TEMAV is defined as a postbaseline value with an increase from baseline to a grade of 2 or higher. For phosphate, a TEMAV was defined as a postbaseline value with an increase from baseline to a grade of 3 or higher. When displaying the incidence of TEMAVs, each subject may be counted once in the laboratory parameter high and in the laboratory parameter low categories, as applicable.

9.7.1.8.4 VITAL SIGNS

Descriptive statistics for vital signs parameters (eg, systolic and diastolic BP, pulse, respiratory rate, temperature, weight) and changes from baseline will be presented by visit and treatment group.

9.7.1.8.5 ELECTROCARDIOGRAMS

For each ECG parameter (including PR interval, RR interval, QRS interval, QT interval, QTc interval (Bazett formula), QTc interval (Fridericia formula), and heart rate), the actual value and change from baseline will be summarized by visit and treatment group using descriptive statistics.

Shift tables will present changes from baseline in ECG interpretation (categorized as normal; abnormal, not clinically significant; and abnormal, clinically significant) to end of treatment.

Maximum postbaseline QTc (Bazett) and QTc (Fridericia) will also be tabulated by treatment group as follows:

- Number (percentage) of subjects in greater than 450 msec, greater than 480 msec, and greater than 500 msec during the treatment, and
- Number (percentage) of subjects with an increment of greater than 30 msec and greater than 60 msec from the baseline visit.

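### The ECG interpretation shift table looks only at end of treatment, so a Week 28 abnormality that improves appears in no planned ECG table; the absolute QTc counts also mix new and pre-existing values

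*Protocol*

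**What the plan says.** The references are to the protocol text for ages 12 to 17 years that includes the echocardiography assessments.

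- **Interpretation.** Section 9.7.1.8.5 states: "Shift tables will present changes from baseline in ECG interpretation (categorized as normal; abnormal, not clinically significant; and abnormal, clinically significant) to end of treatment". No other table of this classification is planned.
- **Interval and rate parameters.** For PR, RR, QRS, QT, both QTc corrections and heart rate, "the actual value and change from baseline will be summarized by visit and treatment group using descriptive statistics".
- **QTc outliers.** "Maximum postbaseline QTc (Bazett) and QTc (Fridericia) will also be tabulated by treatment group as follows": first "Number (percentage) of subjects in greater than 450 msec, greater than 480 msec, and greater than 500 msec during the treatment", then "Number (percentage) of subjects with an increment of greater than 30 msec and greater than 60 msec from the baseline visit". The first count carries no condition on the baseline value.
- **Schedule.** Table 2 places ECGs at Visit 2 (Day 1, baseline), Week 28, Week 52 (end of treatment), Week 56 (end of study) and early discontinuation.
- **Eligibility.** No exclusion criterion in section 9.3.2 sets a QTc limit.
- **Laboratory values, for comparison.** Section 9.7.1.8.3 plans shifts to end of treatment and to follow-up, and adds: "Similar shift tables will also compare the baseline LNH classification to the LNH classification for the highest and lowest value during the treatment period". Its markedly abnormal values must represent an increase in grade from baseline.

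**The concern.** The shift table is the only place where the reader's overall judgement of the tracing is tabulated. A rhythm or conduction finding need not show in an interval summary. If it is rated clinically significant at Week 28 and has improved at Week 52, the table records only the better reading.

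The absolute QTc counts raise a separate, lesser question. With no QTc limit at entry, a subject may be above 450 msec before the first dose and is then counted beside a subject who crossed 450 msec on drug. The two mean different things in a safety table, and the laboratory section of the same protocol separates them.

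What is at stake is the clarity of a descriptive safety display with few tracings per subject. No test or decision rule depends on it.

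**Working it through.** The plan states no figure on this point, so there is none to reproduce. The check applies the stated rules to the stated schedule.

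**1. Where a Week 28 interpretation can appear.** Take a subject read as normal on Day 1, clinically significant at Week 28 and normal at Week 52.

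- Interpretation shift: the endpoint is end of treatment, which Table 2 labels Week 52. The subject is shown as normal to normal.
- By-visit summaries: these are actual values and changes for interval and rate parameters, a format that does not fit a three-level classification. Any interval change at Week 28 enters here as a number; the classification does not.
- QTc outlier table: takes QTc only.

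The Week 28 classification thus enters no ECG table. Two on-treatment interpretations are scheduled and the shift uses one. How many affected subjects are missed depends on persistence, which the documents do not give. If every abnormality persisted to Week 52, none would be missed. If each affected subject had a single abnormal tracing, equally likely at either visit, half would be.

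**2. What the QTc rules capture.** The profiles are assumed, in msec. The last column is the section 9.5.1.5.1 rule that QTc above 450 with an increase above 60 is an adverse event.

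| Day 1 / Wk 28 / Wk 52 | Max | Increase | >450 | >480 | >30 | >60 | AE rule |
|---|---|---|---|---|---|---|---|
| 455 / 456 / 455 (pre-existing, flat) | 456 | 1 | yes | no | no | no | no |
| 440 / 455 / 440 (small, transient) | 455 | 15 | yes | no | no | no | no |
| 420 / 485 / 425 (large, transient) | 485 | 65 | yes | yes | yes | yes | yes |
| 420 / 485 / 485 (large, persistent) | 485 | 65 | yes | yes | yes | yes | yes |

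The large transient rise is counted exactly as the persistent one is. The first two rows, one pre-existing and one new, cannot be told apart in any of these counts. In general, a subject with baseline above 450 − 30 = 420 msec can newly cross 450 without an increase above 30, so the increment counts recover only some new crossers.

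**3. What mixing does to a comparison (illustration; all rates assumed).** Let a share b of each arm be above 450 msec at baseline and stay there, and let new-onset rates among the rest be 2% on placebo and 6% on active. The counted rate is b + (1 − b) × new-onset rate.

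| b | Per 180 | Placebo | Active | Risk ratio | Difference |
|---|---|---|---|---|---|
| 0 | 0 | 2.0% | 6.0% | 3.00 | 4.0 points |
| 1% | 1.8 | 2.98% | 6.94% | 2.33 | 3.96 points |
| 2% | 3.6 | 3.96% | 7.88% | 1.99 | 3.92 points |
| 5% | 9 | 6.9% | 10.7% | 1.55 | 3.8 points |

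The ratio is diluted; the difference barely moves.

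**4. Which cut is affected.** Assume baseline QTc is normal with mean 425, between-subject SD 15 and within-subject SD 13. The total SD is √(225 + 169) = 19.8. The share above 450 is then about 10%, above 480 about 0.3% (roughly half a subject per 180) and above 500 about 0.01%. Under assumptions of this kind the mixing matters at 450 msec and hardly at all at the higher cuts.

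**The case against.** The strongest case is that nothing here is misstated. Absolute thresholds beside increments from baseline form a coherent pair, and the increment counts are the ECG counterpart of the baseline-referenced laboratory rule. Only one intermediate ECG is scheduled. A significant Week 28 tracing can be reported as an adverse event under sections 9.5.1.5.1 and 9.5.1.5.7. Safety is descriptive, and sections 9.7.1 and 9.7.4 leave further detail to the SAP.

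Much of this stands and keeps the point small. It does not remove it. The adverse-event route depends on investigator judgement, except for the QTc rule. Section 9.7.1.8.5 does not leave the tables open: it names the endpoint of the interpretation shift, and a SAP that follows it literally will carry that through.

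A reader might infer four stronger things that the documents do not support:

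- *Transient QTc prolongation is lost.* It is not; the maximum postbaseline value is used.
- *The QTc comparison is biased between arms.* Randomization balances pre-existing values on average.
- *The protocol defines the ECG shift by the last on-treatment tracing.* That definition is given for laboratory values and not repeated for ECG. Under either reading, a subject with a Week 52 on-treatment tracing has Week 28 passed over.
- *Subjects above the cut at baseline should be dropped from the counts.* A subject going from 455 to 478 msec (an increase of 23) would then leave the 450 count, miss the 480 count and miss the 30 msec count, so those with the longest baseline QTc would become less visible.

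**Conclusion.** The point holds as a minor improvement to two tables. The main part follows from the protocol text and schedule alone: for a subject who reaches Week 52, an abnormal Week 28 interpretation that improves is in no planned ECG table, although the laboratory section handles the same situation with extreme-value shifts.

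The secondary part also follows from the text, but only in kind: the absolute counts mix new and pre-existing values, and the increment counts partly offset this. The documents give no QTc mean, SD or prevalence, so no share of pre-existing cases can be stated; the rates shown above are illustrations. The direction is dilution of relative comparisons, chiefly at 450 msec.

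**What to change.** In section 9.7.1.8.5, or in the SAP:

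1. Keep the shift to end of treatment and add, beside it, a shift from baseline to the worst on-treatment interpretation.
2. Keep the all-subject counts above 450, 480 and 500 msec and add a cross-tabulation by arm of baseline QTc category (up to 450, above 450 to 480, above 480 to 500, above 500) by maximum on-treatment category, for each correction formula. New and pre-existing values are then both visible and nobody is removed.
3. While editing, say whether the Week 56 tracing counts, since the QTc wording refers both to postbaseline and to during treatment.

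The cost is two extra descriptive panels. All the data are already scheduled for collection, and no existing table is withdrawn.

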9.7.1.8.6 OTHER SAFETY ANALYSES

Other safety assessments including adolescent growth evaluations using 95th percentile CDC growth charts and bone age using x-ray of the hand, sexual maturation as measured in Tanner Staging, neuromuscular sign assessment for serotonin syndrome, signs and symptoms of priapism and prolactinemia, study drug effect on cognitive function assessed by WRAML-2, assessment of suicidality using C-SSRS, and depression assessment using PHQ-9 will be summarized by treatment group at each scheduled visit. For echocardiographic assessments, the proportion of subjects who develop FDA-defined valvulopathy, the proportion of subjects who develop pulmonary hypertension (defined as when a subject's SPAP is ≥ 40 mmHg evaluated by echocardiograph], and change from baseline in SPAP will also be summarized by treatment group at Week 28 and Week 52.

9.7.2 Determination of Sample Size

The proposed sample size is based on the comparison of the primary efficacy endpoint, change from Baseline in BMI at Week 52 between the Belviq XR 20-mg treatment group and placebo group. Assuming a SD of 2.2 kg/m² and a 40% dropout rate, a sample size of 360 subjects in a 1:1 ratio (n=180 in the Belviq XR 20-mg treatment group; n=180 in the placebo group) will have at least 90% power to detect a treatment difference of 1 kg/m² in BMI, using a 2-sided t-test with $\alpha=0.05$. Assuming the proportion of subjects achieving at least a 5% BMI reduction at Week 52 is 20% for the placebo group and a 40% dropout rate, this sample of 360 subjects (180 subjects for Belviq XR 20 mg and 180 subjects for placebo) will also have greater than 85% power to detect an absolute difference of 20% between the Belviq XR 20-mg group and placebo group, using a 2-sided Fisher's Exact test with $\alpha=0.05$. The assumption used in the sample size calculation is based on the 2 pivotal lorcaserin studies, APD356-009 and APD356-011 in obese and overweight non-diabetic adult subjects.

9.7.3 Interim Analysis

No interim analysis is planned for this study.

9.7.4 Other Statistical/Analytical Issues

Further statistical and analytical issues will be discussed in the SAP.

9.7.5 Procedure for Revising the Statistical Analysis Plan

If the SAP needs to be revised after the study starts, the sponsor will determine how the revision impacts the study and how the revision should be implemented. The details of the revision will be documented and described in the clinical study report.

11 PROCEDURES AND INSTRUCTIONS (ADMINISTRATIVE PROCEDURES)

11.1 Changes to the Protocol

Any change to the protocol requires a written protocol amendment or administrative change that must be approved by the sponsor before implementation. Amendments specifically affecting the safety of subjects, the scope of the investigation, or the scientific quality of the study require submission to health or regulatory authorities as well as additional approval by the applicable IRBs/IECs. These requirements should in no way prevent any immediate action from being taken by the investigator, or by the sponsor, in the interest of preserving the safety of all subjects included in the study. If the investigator determines that an immediate change to or deviation from the protocol is necessary for safety reasons to eliminate an immediate hazard to the subjects, the sponsor's medical monitor and the IRB/IEC for the site must be notified immediately. The sponsor must notify the health or regulatory authority as required per local regulations.

Protocol amendments that affect only administrative aspects of the study may not require submission to health or regulatory authority or the IRB/IEC, but the health or regulatory authority and IRB/IEC should be kept informed of such changes as required by local regulations. In these cases, the sponsor may be required to send a letter to the IRB/IEC and the Competent Authorities detailing such changes.

11.2 Adherence to the Protocol

The investigator will conduct the study in strict accordance with the protocol (refer to ICH E6, Section 4.5).

11.3 Monitoring Procedures

The sponsor's/CRO's CRA will maintain contact with the investigator and designated staff by telephone, letter, or email between study visits. Monitoring visits to each site will be conducted by the assigned CRA as described in the monitoring plan. The investigator will allow the CRA to inspect the clinical, laboratory, and pharmacy facilities to assure compliance with GCP and local regulatory requirements. The CRFs and subject's corresponding original medical records (source documents) are to be fully available for review by the sponsor's representatives at regular intervals. These reviews verify adherence to study protocol and data accuracy in accordance with local regulations. All records at the site are subject to inspection by the local auditing agency and IRB/IEC review.

In accordance with ICH E6, Section 1.52, source documents include, but are not limited to the following:

- Clinic, office, or hospital charts
- Copies or transcribed health care provider notes which have been certified for accuracy after production
- Recorded data from automated instruments such as IxRS, x-rays, and other imaging reports, (eg, sonograms, computerized tomography scans, magnetic resonance images, radioactive images, ECGs, rhythm strips, EEGs, polysomnographs, pulmonary function tests) regardless of how these images are stored, including microfiche and photographic negatives
- Pain, quality of life, or medical history questionnaires completed by subjects
- Records of telephone contacts
- Diaries or evaluation checklists
- Drug distribution and accountability logs maintained in pharmacies or by research personnel
- Laboratory results and other laboratory test outputs (eg, urine pregnancy test result documentation and urine dip-sticks)
- Correspondence regarding a study subject's treatment between physicians or memoranda sent to the IRBs/IECs
- CRF components (eg, questionnaires) that are completed directly by subjects and serve as their own source

11.4 Recording of Data

A CRF is required and must be completed for each subject by qualified and authorized personnel. All data on the CRF must reflect the corresponding source document, except when a section of the CRF itself is used as source document. Any correction to entries made on the CRF must be documented in a valid audit trail where the correction is dated, the individual making the correction is identified, the reason for the change is stated, and the original data are not obscured. Only data required by the protocol for the purposes of the study should be collected.

The investigator must sign each CRF. The investigator will report the CRFs to the sponsor and retain a copy of the CRFs.

11.5 Identification of Source Data

All data to be recorded on the CRF must reflect the corresponding source documents.

11.6 Retention of Records

The circumstances of completion or termination of the study notwithstanding, the investigator is responsible for retaining all study documents, including but not limited to the protocol, copies of CRFs, the Investigator's Brochure, and regulatory agency registration documents (eg, Form FDA 1572 ICFs, and IRB/IEC correspondence). In addition, the sponsor will send a list of treatment codes by study subject to the investigator after the clinical database for this study has been locked. The site should plan to retain study documents, as directed by the sponsor, for at least 2 years after the last approval of a marketing application in an ICH region and until there are no pending or contemplated marketing applications in an ICH region or at least 3 years have elapsed since the formal discontinuation of clinical development of the investigational product.

It is requested that at the completion of the required retention period, or should the investigator retire or relocate, the investigator contact the sponsor, allowing the sponsor the option of permanently retaining the study records.

11.7 Auditing Procedures and Inspection

In addition to the routine monitoring procedures, the sponsor's Clinical Quality Assurance department conducts audits of clinical research activities in accordance with the sponsor's SOPs to evaluate compliance with the principles of ICH GCP and all applicable local regulations. If a government regulatory authority requests an inspection during the study or after its completion, the investigator must inform the sponsor immediately.

11.8 Handling of Study Drug

All study drugs will be supplied to the PI (or a designated pharmacist) by the sponsor. Drug supplies must be kept in an appropriate secure area (eg, locked cabinet) and stored according to the conditions specified on the drug labels. Investigational product will be stored in accordance with the DEA Regulations for Scheduled III - V Drugs and labeled storage conditions. The investigator (or a designated pharmacist) must maintain an accurate record of the shipment and dispensing of the study drug in a drug accountability ledger, a copy of which must be given to the sponsor at the end of the study. An accurate record of the date and amount of study drug dispensed to each subject must be available for inspection at any time. The CRA will visit the site and review these documents along with all other study conduct documents at appropriate intervals once study drug has been received by the site.

All drug supplies are to be used only for this study and not for any other purpose. The investigator (or site personnel) must not destroy any drug labels or any partly used or unused drug supply before approval to do so by the sponsor. At the conclusion of the study and as appropriate during the study, the investigator (or a designated pharmacist) will return all used and unused drug containers, drug labels, and a copy of the completed drug disposition form to the sponsor's CRA.

11.9 Publication of Results

All manuscripts, abstracts, or other modes of presentation arising from the results of the study must be reviewed and approved in writing by the sponsor in advance of submission pursuant to the terms and conditions set forth in the executed Clinical Trial Agreement between the sponsor/CRO and the institution/investigator. The review is aimed at protecting the sponsor's proprietary information existing either at the date of the commencement of the study or generated during the study.

The detailed obligations regarding the publication of any data, material results, or other information, generated or created in relation to the study shall be set out in the agreement between each investigator and the sponsor or CRO, as appropriate.

11.10 Disclosure and Confidentiality

The contents of this protocol and any amendments and results obtained during the study should be kept confidential by the investigator, the investigator's staff, and the IRB/IEC and will not be disclosed in whole or in part to others, or used for any purpose other than reviewing or performing the study, without the written consent of the sponsor. No data collected as part of this study will be used in any written work, including publications, without the written consent of the sponsor. These obligations of confidentiality and non-use shall in no way diminish such obligations as set forth in either the Confidentiality Agreement or Clinical Trial Agreement executed between the sponsor/CRO and the institution/investigator.

All persons assisting in the performance of this study must be bound by the obligations of confidentiality and non-use set forth in either the Confidentiality Agreement or Clinical Trial Agreement executed between the institution/investigator and the sponsor/CRO.

11.11 Discontinuation of Study

The sponsor reserves the right to discontinue the study for medical reasons or any other reason at any time. If a study is prematurely terminated or suspended, the sponsor will promptly inform the investigators/institutions and regulatory authorities of the termination or suspension and the reason(s) for the termination or suspension. The IRB/IEC will also be informed promptly and provided the reason(s) for the termination or suspension by the sponsor or by the investigator/institution, as specified by the applicable regulatory requirement(s).

The investigator reserves the right to discontinue the study should his/her judgment so dictate. If the investigator terminates or suspends a study without prior agreement of the sponsor, the investigator should inform the institution where applicable, and the investigator/institution should promptly inform the sponsor and the IRB/IEC and provide the sponsor and the IRB/IEC with a detailed written explanation of the termination or suspension. Study records must be retained as noted above.

